Indeed, the aggressiveness of these surgeries has yielded grade 3 or worse complication rates, which include death, in the range of 15-22%, as reported from high-volume medical centers [3,4]. Such notable complication rates underscore the need to evaluate strategies not only to lessen postoperative complications but also to improve long-term survival by means of exploring interventions to enhance postoperative recovery and thereby enable the prompt administration of chemotherapy.

1.3 Capitalizing on Therapeutic Modalities with Demonstrated Efficacy: The Timely Administration of Post-Operative Chemotherapy. Mahner and others recently demonstrated that timely administration of postoperative chemotherapy to patients with ovarian cancer improves outcomes [5]. These investigators examined individual patient data from 3326 ovarian cancer patients who had participated in 3 prospective phase III trials. Within this large cohort, the median time to chemotherapy was 19 days (range 1, 56 days), but starting chemotherapy sooner appeared to confer a survival advantage. Among patients who had had an optimal debulking surgery, a longer time to chemotherapy initiation was associated with a poorer survival (per week delay hazard ratio=1.87; 95% confidence interval 1.005, 1.176; p=0.038). Indeed, a one week delay in

chemotherapy yielded an 8.7% increase in mortality in patients who had received an optimal debulking surgery. These data point to the importance of the timely administration of chemotherapy in patients who have undergone an optimal debulking surgery for ovarian cancer.

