2.2 Secondary Efficacy

- 2.21 To compare the surgical complication rates between oral SBI vs. placebo up to 1 month post-surgery (safety endpoint).
- 2.22 To compare the QOL, as derived from the previously-validated Symptom Distress Scale, the PQL (Postoperative Quality of Life questionnaire), and the uniscale (overall QOL item) between patients receiving oral SBI vs. placebo.
- 2.23 To compare the grade 2 or worse adverse event rates for patients receiving oral SBI vs. placebo.
- 2.24 To characterize the adverse event profile of oral SBI in postoperative gynecological cancer patients (safety endpoint).
- 2.25 To compare supplement adherence between patients receiving oral SBI vs. placebo.

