be converted to 100 and a score of 0 will remain as 0. This QOL will be measured weekly for the entire 12 week length of the study and at the end of the intervention. QOL improvement will be defined as at least a 10 point increase in the QOL score from baseline, on the percentage scale. This 10 point change represents a clinically meaningful improvement in QOL based on work done by Jeff Sloan [17]. The date at which the QOL score is first known to increase by at least 10 from baseline (on the 100 point scale), will be considered the event date for the purpose of analysis. Patients without at least a 10 point increase in QOL from baseline, will be censored on their last QOL evaluation date up to a maximum of 12 weeks. We will enter a total of 70 evaluable patients (35 per arm) using a 1:1 randomization scheme. The primary analysis will be a comparison of oral SBI vs. placebo using a two-sided log-rank test between the 2 Kaplan-Meier curves [18]. This analysis will take place after an approximate 16 month accrual period, and after 66 total events across both arms combined (which should happen after about 12 weeks of follow-up in all evaluable patients). Additionally, we assume a constant accrual rate over the course of the study, and that no patients will drop-out of the study, since historically the lost to follow-up rate is <1%. To determine the appropriate sample size of 35 evaluable patients per arm, we assumed exponential survival and that the median time-to-QOL improvement is around 3 weeks in the oral SBI arm and 6 weeks in the placebo arm (HR=2). This hazard ratio is based on our institution's data which shows that patients often begin postoperative chemotherapy 6 weeks after surgery. These assumptions yield 80% power to detect a significant difference between the arms using a 2-sided log-rank test at alpha=0.05. All patients who meet the eligibility criteria, sign the consent form, and are randomized, will be considered evaluable for this endpoint. All eligible patients will be followed a maximum of 12 weeks. If the 2-sided log-rank test p-value is < 0.05 showing significantly shortened time-to-QOL improvement in the oral SBI arm as compared to placebo, further study will be warranted. Of course, any final decisions will be based on all primary and secondary endpoints.

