- 16.2 Sample Size: The study design to be utilized is fully described in Section 16.11 (see above). There will be 35 evaluable patients randomized to each arm of this study. We anticipate accruing an additional 15 patients to each arm to account for ineligibility, cancellation, major intervention violation, or other reasons. Therefore, maximum accrual is 100 patients (50 per arm).
- 16.3 Accrual Time and Study Duration: The anticipated accrual rate is approximately 4-5 patients per month. Therefore, the accrual period for this randomized Pilot study is expected to be around 24 months. The final analysis can begin approximately 28 months after the trial begins, i.e., as soon as the last patient registered has been observed for 4 months.
- 16.4 Other Considerations: Adverse events as well as scientific discoveries or changes in standard care will be taken into account in any decision to terminate the study.

16.5 Data & Safety Monitoring:

16.51 The principal investigator(s) and the study statistician will review the study at least twice a year to identify accrual, adverse event, and any endpoint problems that might be developing. The trial is monitored continually by the study team who are notified of every grade 4 and 5 event in real time. The Mayo Clinic Cancer Center (MCCC) Data Safety Monitoring Board (DSMB) is responsible for reviewing accrual and safety data for this trial at least twice a year, based on reports provided by the MCCC Statistical Office.

16.52 Adverse Event Stopping Rules: The stopping rules specified below are based on the knowledge available at study development. We note that the Adverse Event Stopping Rule may be adjusted in the event of either (1) the study re-opening to accrual or (2) at any time during the conduct of the trial and in consideration of newly acquired information regarding the adverse event profile of the intervention(s) under investigation. The study team may choose to suspend accrual because of unexpected adverse event profiles that have not crossed the specified rule below. CTCAE v4.0 will be used to determine grading for these stopping rules.

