We expect about 10% of patients to experience grade 3 or worse adverse events (at least possibly related to the study intervention). In addition, we expect less than 1% of patients to experience a Grade 5 adverse event, at least possibly related to the study intervention. Accrual will be temporarily suspended to this study if at any time we observe adverse events that satisfy any of the following within each arm separately (i.e. if any of the following occur in arm A or arm B, we will suspend accrual to the trial):

- If at any time 4 or more in the first 20 treated patients (or 20% or more after the first 20) experience a Grade 3 or worse adverse event (possibly, probably, or definitely related to the intervention).
- If at any time, 1 patient experiences a grade 5 adverse event (possibly, probably, or definitely related to the intervention).

We note that we will review all Grade 5 adverse events on a case-by-case basis as well (regardless of attribution), and may suspend accrual after just one Grade 5 event, if we feel it is necessary for patient safety.

16.6 Definitions and Analyses of Secondary Endpoints: All these endpoints will be assessed individually and will also be compared between the 2 arms. Monthly phone calls may be used to collect the secondary endpoint information for each patient, including adverse events, surgical complications, and other data (e.g. patient reported weight, intervention compliance, etc.). We will be assessing, reporting on, and potentially analyzing all the data collected from these monthly telephone calls.

16.61 Adverse Events: All eligible patients who have initiated therapy will be considered evaluable for adverse event analyses. The maximum grade for each type of adverse event will be recorded for each patient up to 16 weeks post-randomization (12 weeks of intervention + 1 month post-intervention observation timepoint), and frequency tables will be reviewed to determine adverse event

patterns. The overall adverse event rates for grade 2 or higher adverse events, will be compared using Chi-Square or Fisher's Exact tests. In addition, the surgical complication rates (up to 1 month post-surgery) will also be compared between the 2 arms using Chi-Square or Fisher's Exact tests.

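### Section 16.61 compares surgical complications and grade 2 or higher adverse events by significance test alone; a risk difference with a 95% confidence interval should be the main result.

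*Combined protocol and SAP*

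**What the plan says.** Goal 2.21 reads "To compare the surgical complication rates between oral SBI vs. placebo up to 1 month post-surgery (safety endpoint". Goal 2.23 adds a between-arm comparison of grade 2 or worse adverse events, without the safety label.

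Section 16.61 gives the analysis: "the surgical complication rates (up to 1 month post-surgery) will also be compared between the 2 arms using Chi-Square" or Fisher's exact tests. Grade 2 or higher adverse event rates get the same tests. The section also plans frequency tables of maximum grade. It names no risk difference, risk ratio, confidence interval or margin, and it gives no alpha, power or precision for these comparisons.

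Section 16.11 sets the criterion for further study as a log-rank p-value below 0.05 on the primary endpoint, and then adds that "any final decisions will be based on all primary and secondary endpoints".

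On size, Section 16.2 says "There will be 35 evaluable patients randomized to each arm of this study", and with allowance for losses "maximum accrual is 100 patients (50 per arm". Section 1.2 supplies the only complication rate in the document. It cites high-volume centres where aggressive ovarian surgery "has yielded grade 3 or worse complication rates, which include death, in the range of 15-22" per cent.

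**The concern.** A test of no difference answers one question: are the data surprising if the arms have equal rates? For a safety comparison the useful question is how much excess harm the data can rule out. A p-value above 0.05 does not answer that, and in a trial of this size it can sit beside a large observed excess.

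This matters because the study is meant to lay the groundwork for a larger trial, and the secondary endpoints are said to feed that decision. If complications are summarised only as not significantly different, whoever plans the next trial cannot see whether a 5-point or a 30-point increase is still open.

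**Working it through.** **The plan's own figure.** No power or precision is stated for complications, so there is nothing to reproduce for this endpoint. The trial is sized on the primary log-rank test. With Schoenfeld's formula, events = 4(1.960 + 0.842)² / (ln 2)² = 65.4, rounded up to 66. This matches the 66 events for 80% power at HR = 2 in Section 16.11.

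**Inputs.**
- n per arm: 35 (planned evaluable) and 50 (maximum), from Section 16.2. Section 16.61 counts eligible patients who started therapy, so 50 is a ceiling.
- Placebo rate: 15% and 22%, from Section 1.2. Applying them to this trial is an assumption.
- SBI rate: double the placebo rate, that is 30% and 44%. This is an illustrative harm.
- Two-sided alpha 0.05. The plan states it for the primary endpoint only; it is assumed here.

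**Chance of missing a doubling.** Enumerate every pair of counts (i, j):

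miss = 1 − Σᵢ Σⱼ Bin(i; n, p) · Bin(j; n, 2p) · 1{test p-value < 0.05}

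| n per arm | Rates | Fisher misses | Uncorrected chi-square misses |
|---|---|---|---|
| 35 | 15% vs 30% | 76.7% | 68.3% |
| 35 | 22% vs 44% | 58.5% | 48.8% |
| 50 | 15% vs 30% | 64.6% | 55.7% |
| 50 | 22% vs 44% | 42.3% | 34.6% |

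The range is 49-77% at 35 per arm and 35-65% at 50. A 10-point increase (15% to 25%, or 22% to 32%) is missed 76-90% of the time across both tests and both sizes.

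**What an interval would show when observed rates are equal.** Half-width = 1.96 √(2p(1 − p)/n):
- n = 35: 1.96 √(2 × 0.15 × 0.85/35) = 16.7 points; with p = 0.22, 19.4 points.
- n = 50: 14.0 points; with p = 0.22, 16.2 points.

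Newcombe intervals for whole counts are close: ±17.1 (5/35 in each arm), ±19.4 (8/35), ±14.7 (8/50) and ±16.2 (11/50). In all four cases the 95% interval for the risk ratio still includes 2. The narrowest is 0.48 to 2.09, at 11/50 in each arm.

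**What the two forms of report look like.** Suppose 5/35 on placebo and 10/35 on SBI, an observed doubling. Chi-square = 70(10 × 30 − 5 × 25)² / (35 × 35 × 15 × 55) = 2.12, below the 3.84 needed, so the test is not significant. The Wilson limits are 6.3% to 29.4% for 5/35 and 16.3% to 45.1% for 10/35. The difference is 28.6 − 14.3 = 14.3 points. The Newcombe limits are:
- lower: 14.3 − √((28.6 − 16.3)² + (29.4 − 14.3)²), about −5 points
- upper: 14.3 + √((45.1 − 28.6)² + (14.3 − 6.3)²), about +33 points

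The test reports no significant difference. The interval reports that an excess of up to about 33 points remains compatible with the data.

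**Grade 2 or higher adverse events.** The documents give no expected rate for these, so no miss rate is computed. The reporting gap is the same.

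**The case against.** The strongest reply is that this is a pilot by its own description (Section 16.1). Low power on a secondary endpoint is expected, and nothing in the plan misuses the result. That stands, and the point is not a request for more patients. By the usual pooled formula, 80% power for a doubling would need about 121 per arm (15% vs 30%) or 71 per arm (22% vs 44%), which is outside the purpose of this study.

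A reader might infer that the plan will treat p > 0.05 as proof of safety. The documents do not support that. No sentence says so, the explicit criterion in Section 16.11 concerns the primary endpoint, and the sentence about all endpoints describes an open judgement rather than a rule.

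A reader might also infer that a null result would be empty, or that a doubling would usually go undetected. Neither holds throughout. Equal observed rates would exclude differences beyond roughly 14 to 19 points. At 50 per arm with 22% vs 44%, power is 58% (Fisher) or 65% (chi-square).

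Other safeguards exist: per-arm suspension rules for related grade 3 or worse and grade 5 events, case-by-case review of every grade 5 event, real-time notice of grade 4 and 5 events, and DSMB review at least twice a year. Safety does not rest on this one test. However, the suspension rules count only events attributed to the intervention and act within each arm, so they do not estimate a between-arm difference in complications.

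The arms' rates will be compared, so with their denominators anyone could compute the interval afterwards. That is true, but an interval planned in advance as the main result is harder to leave out.

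The 15-22% rate is also a weak input. It describes grade 3 or worse complications of aggressive ovarian surgery. The trial admits laparoscopic and non-ovarian cases, the endpoint is not limited to grade 3 or worse, and patients may register up to 7 days after surgery and start product up to 7 days later. The trial's rate could lie on either side. At an assumed 10% vs 20%, 70-87% of doublings would be missed.

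**Conclusion.** The point holds as a gap in how two safety-related comparisons are reported. Section 16.61 plans a test without an estimate or interval, so the planned result cannot show what size of harm remains possible. Under an assumed placebo rate of 15-22% and two-sided alpha 0.05, a true doubling of surgical complications is missed 49-77% of the time at 35 per arm and 35-65% at 50. Equal observed rates leave about ±17 to 19 points and ±14 to 16 points respectively. These figures move with the placebo rate, which the documents do not establish for this population.

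The primary analysis is unaffected. This is a low-cost improvement, not a defect that undermines the trial. It does not support tying the Section 16.11 decision to the upper limit of the interval: the plan gives no margin, and even equal observed rates in the examples above would not exclude a doubling.

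**What to change.** In Section 16.61, for both surgical complications and grade 2 or higher adverse events:
- Make the main result the SBI-minus-placebo risk difference with a two-sided 95% confidence interval, naming the method (Newcombe, for example), alongside the count and denominator in each arm.
- Keep the chi-square or Fisher p-value as supplementary.
- Add a sentence such as: A non-significant test will not be taken as evidence that SBI does not increase complications.

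The cost is a few lines of text and one interval per comparison, with no new data or patients. The drawback is that the safety statement will look less favourable, because the interval will be wide.

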4.0 Test Schedule

Tests and procedures	Active Monitoring Phase				Observation/crossover (ends after 16 weeks of total study participation)
	≤21 days prior to randomization	Day 1 of Cycle 2 and 3 (+/- 3 days)	Weekly from registration for 12 weeks total	At the end of intervention (+/- 3 days)	
Patient assessment (includes weight**)	X				
Adverse event assessment	X	X**		X**	X**
Pregnancy test ¹ (Serum)	X				
Hematology group					
HgB					
WBC	X				
PLT					
ANC					
Chemistry group					
Creatinine	X				
Patient Questionnaire					
Booklets ² , (Appendix 2-5)	X		X	X	X
Blood specimens (see Section 14.0) ^{3,R}	X	X*			

1. For women of childbearing potential only. Must be done ≤7 days prior to registration.
2. Patient questionnaire booklets **must** be used; copies are not acceptable for this submission. Patients are required to fill out the questionnaires at baseline, and weekly for the duration of study participation, (16 weeks total, includes patients who never started therapy).
3. Blood specimens will be collected and submitted at baseline. Kits are required. Baseline blood specimen is to be collected after consent and prior to patient receiving study agent.

R Research funded (see Section 19.0)

*These blood draws are optional but strongly recommended.

** If patient cannot return, this assessment can be done by phone by the study coordinator (includes patient reported weight). However, study questionnaires must be mailed back.

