16.62 **Intervention Compliance:** Intervention compliance will be assessed using the Compliance Questionnaire in Appendix V. The frequency and percentage for each Compliance Questionnaire category will be summarized descriptively by cycle and by intervention arm. In addition, cycle by cycle compliance data will be compared between the 2 arms using a Chi-square test.

16.63 **Quality of Life:** QOL will be measured with 3 QOL tools. For the primary endpoint, the total score from the 14-item Postoperative Quality of Life (PQL) tool [15] (Appendix II) will be used (16.11). As a secondary analysis, all 14 of the individual items from the PQL tool (Appendix II), along with the 4 additional items after the PQL questions (Appendix II) will be analyzed and compared between the 2 intervention arms. In addition, the time-to-QOL improvement will be compared between the 2 arms for any increase (> 0) from baseline for the total score from the PQL tool. This will be done descriptively, and using a Kaplan-Meier analysis [18], where any increase in the QOL from baseline will represent an event. QOL will also be measured using the Uniscale (Appendix III), and the previously-validated Symptom Distress Scale (SDS; Appendix IV). These QOL tools will measure QOL at baseline, every week up to 12 weeks post-randomization, and at the end of intervention. Differences between post-randomization and baseline QOL scores will be analyzed and compared between the 2 arms using a Wilcoxon Rank-sum test. Also, other graphical and statistical methods will be used to compare the QOL and time-to-QOL improvement between the 2 arms. As an exploratory analysis, we will also collect QOL data on patients who do not start intervention/placebo or discontinue intervention/placebo early and are willing to be followed per the test schedule (Section 4). This analysis will be descriptive in nature to see if these patients have a poorer QOL than patients who stay on study.

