Appendix V Compliance Questionnaire

Please answer the question below about how often you took your study treatment during the past cycle.

Check only one box that reflects your response.

Over the past week, I took my study supplement:

- Always or almost always
- Usually
- Occasionally
- Rarely
- Never or almost never

Patient reported weight: _____ Unit of measure: (check one) _____ lbs. _____ kg

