Appendix VI Nurse/CRA Phone Worksheet**Phone Contact Guide**

NOTE: This should serve only as a guide to collect information while on the phone with the patient and does not replace any data forms which are required to be filled out. Do not fill out and submit this form, rather submit the data forms using the RDE system.

1. Call patient on day 2 of cycle 1 to reinforce daily questionnaire completion and answer any questions they may have. If day 2 falls on a weekend or holiday, you may call the patient on the next business day. .
2. Call patient on day 2 of cycle 2 and day 2 of cycle 3 to assess compliance and answer questions below. Note: phone calls are only required for patients not returning to the accruing institution for monthly therapy/assessment. Patients returning to the accruing institution for monthly therapy should be seen and assessed in person. Patients not returning to the accruing institution for therapy should be assessed via phone.

1. Items to document include:

- Date of phone call.
- Study cycle.
- Compliance: Has the participant completed the questionnaire booklet each week (always, usually, rarely, never)? If not always, document reason(s) and reinforce weekly booklet completion. If never, document reason(s) in the Patient Questionnaire Booklet Compliance Form and reinforce weekly booklet completion.
- Side effects

Abdominal pain

Bloating

Diarrhea

Baseline number of stools per day

Flatulence

Nausea

Vomiting

Fatigue

Wound infection

Wound complication

Wound dehiscence

- Has the patient been taking the agent (Always or almost always; Usually; Occasionally; Rarely; Never or almost never)?

4. Reinforce compliance with booklet and remind participant to return booklet to study staff at their next appointment or in the envelope provided at the end of each 4 weeks.

5. Reinforce completion of questionnaires. NOTE: if patient decides to stop study early, ask them to fill out the questionnaires at the end of the booklet and return in the envelope provided.

7. Items to document include:

- Date of phone call.
- Study cycle.
- Patient reported weight. (lbs/kg)
- Has cancer therapy started (yes/no). If yes, chemo/RT/hormonal/other, specify-List start date of each.
- Compliance questionnaire

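### The chi-square test in 16.62 ignores the order of the five compliance answers and loses power for a one-directional shift, and Appendix V asks about two recall periods with one tick box

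*Combined protocol and SAP*

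**What the plan says.** Comparing supplement adherence between arms is secondary goal 2.25. Section 16.62 covers it in three sentences:

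- Instrument: "Intervention compliance will be assessed using the Compliance Questionnaire in Appendix V".
- Summary: "The frequency and percentage for each Compliance Questionnaire category will be summarized descriptively by cycle and by intervention arm".
- Test: "cycle by cycle compliance data will be compared between the 2 arms using a Chi-square test". No trend or ordinal version is named.

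Appendix V is a single item with five answers, from always or almost always down to never or almost never. Its instruction reads "Please answer the question below about how often you took your study treatment during the past cycle". The item stem directly below reads "Over the past week, I took my study supplement". One box is ticked.

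Two routes could supply the answer:

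- **Booklet.** The Section 4.0 test schedule lists Appendices 2 to 5 in the questionnaire-booklet row, and its footnote says "Patients are required to fill out the questionnaires at baseline, and weekly for the duration of study participation".
- **Phone or visit.** Appendix VI says "Call patient on day 2 of cycle 2 and day 2 of cycle 3 to assess compliance and answer questions below", with in-person assessment for patients who return to the site. It records the same scale: "Has the patient been taking the agent (Always or almost always; Usually; Occasionally; Rarely; Never or almost never". Section 16.6 also says that monthly calls may collect compliance.

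No section says which route feeds the 16.62 analysis, or how several answers in one cycle become one value.

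**The concern.** There are two separate problems.

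**The test.** If patients on one arm take less of the product, answers should move along the scale in one direction. A Pearson chi-square on a 2×5 table spreads its 4 degrees of freedom over every pattern of difference and does not use the order. A rank test concentrates on a shift. Several cells will also be sparse at 35 per arm. The plan already uses the Wilcoxon rank-sum test for QOL changes (16.63) and biomarkers (16.64), so the choice in 16.62 is out of line with its neighbours.

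**The form.** A cycle is 28 days. A patient who took every packet for three weeks and none in the fourth can truthfully answer near the top of the scale for the cycle and at the bottom for the week. Once the box is ticked, no analysis can recover which period the patient meant. This is the more lasting of the two problems, because the test can still be changed at analysis and the recorded answer cannot.

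**Working it through.** **Plan's own figures.** No power, effect size or alpha is stated for compliance. The number of patients comes from the primary endpoint (16.11): hazard ratio 2, two-sided alpha 0.05, 80% power. By Schoenfeld's formula, events = 4 × (1.960 + 0.842)² / (ln 2)² = 4 × 7.85 / 0.480 ≈ 65.4, so 66, as stated. The 35 evaluable patients per arm are taken from there. The maximum is 50 per arm (16.2).

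**Assumptions (not in the documents).** One answer per patient. Placebo distribution p = 55/20/10/5/10% from best to worst adherence. The other arm has a common odds ratio (OR) on every cumulative split: new odds = OR × old odds.

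**Shifted distributions.** The cumulative placebo proportions 0.55, 0.75, 0.85 and 0.90 have odds 1.222, 3, 5.667 and 9.

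- OR 0.4: odds 0.489, 1.2, 2.267, 3.6; cumulative 0.328, 0.545, 0.694, 0.783; q = 32.8/21.7/14.8/8.9/21.7%.
- OR 0.3: odds 0.367, 0.9, 1.7, 2.7; cumulative 0.268, 0.474, 0.630, 0.730; q = 26.8/20.5/15.6/10.0/27.0%.

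**Sparse cells.** With no difference, expected counts per arm are 35 × p = 19.25, 7, 3.5, 1.75 and 3.5. Three of five are below 5, so 6 of the 10 cells.

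**Chi-square power, analytic.** The noncentrality is λ = n Σ (p − q)² / (p + q). At OR 0.4, λ = 35 × (0.0559 + 0.0007 + 0.0094 + 0.0108 + 0.0434) = 35 × 0.1202 ≈ 4.2. With 4 df at 0.05 this gives about 34%. At OR 0.3, λ ≈ 7.15, giving about 55%.

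**Simulation (6000 trials per scenario, two-sided 0.05, tie-corrected Wilcoxon; ranges are over repeat runs).**

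| OR | Chi-square, 4 df | Wilcoxon |
|---|---|---|
| 0.4 | 32–34% | 53% |
| 0.3 | 55–57% | 78–79% |

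**Other assumed distributions, 35 per arm (chi-square to Wilcoxon).** Here OR 2, 3 and 4 mean the odds of better adherence are divided by that number.

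| Reference distribution | OR 2 | OR 3 | OR 4 |
|---|---|---|---|
| 70/15/7/4/4% | 15% to 30% | 38% to 64% | 64% to 84% |
| 50/20/12/8/10% | 20% to 36% | 48% to 71% | 70% to 89% |
| 30/25/20/15/10% | 21% to 37% | 50% to 73% | 71% to 89% |

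The gain is about 15 to 26 points. At 50 per arm and OR 3, power is 58–68% for chi-square and 80–87% for Wilcoxon.

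**Validity.** With one answer per patient and no true difference, the chi-square rejects in about 5% of trials under the 50/20/12/8/10% and 30/25/20/15/10% distributions, and in 2.9% under the sparse 70/15/7/4/4% one. It does not inflate error.

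**Non-monotone case.** For 50/20/12/8/10% against 50/5/30/13/2% at 35 per arm, power is 61% for chi-square and 6% for Wilcoxon. The ranking of the tests reverses.

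**How often the form is given.** Read literally, the schedule puts Appendix V in a weekly booklet, about four answers per cycle. The same row is also ticked at baseline, before any supplement is taken, and in the observation phase, after it has stopped. A compliance item makes little sense at either, so the label may be generic. Appendix VI and Section 16.6 support a once-per-cycle route. The text does not settle which applies.

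**The case against.** The strongest reply has four parts.

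1. **A chi-square is valid and the wording is loose.** Section 16.62 neither specifies a 2×5 table nor excludes a trend or collapsed version. Collapsing to the top category against the rest gives 44% at OR 0.4 and 68% at OR 0.3, which recovers about half of the loss. This stands as a limit on the size of the point. But no such version is named, and the plain reading is the unordered test.
2. **The effects are large and assumed.** An OR of 0.4 takes the top category from 55% to about 33%, a big gap for matched packets, and even Wilcoxon then has only about 53% power. This stands. The comparison shows relative efficiency and makes no forecast.
3. **Interpreting a null primary result needs the level of adherence more than a p-value.** The category table by cycle and arm already gives that level. This stands, and it is why the table should be kept.
4. **This is a pilot, and compliance is one of five secondary goals.** This stands and sets the severity.

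A reader might also infer that the plan inflates type I error by putting four correlated weekly answers per patient into one chi-square. If that were done, type I error would be about 10%, 15% and 22% at assumed within-patient correlations of 0.3, 0.5 and 0.7. The documents do not support this as a consequence of the plan. Section 16.62 speaks of cycles, Section 16.6 and Appendix VI provide a once-per-cycle answer, and nothing says that weekly answers will be stacked as independent rows.

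**Conclusion.** The point holds as a minor one, in two parts.

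First, the unordered chi-square is valid with one answer per patient but inefficient for a one-directional shift. The loss is about 20 percentage points in the main scenarios and 15 to 26 across the other distributions tried at 35 per arm. These sizes rest on assumed distributions, a common odds ratio and one answer per patient. The direction was the same in every one-directional case tried and reverses for a non-monotone difference.

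Second, Appendix V contradicts itself on the recall period, and the plan does not identify the source or the single value that represents a cycle. This part needs no assumption.

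It would go too far to conclude that the compliance test is invalid, that its error rate is inflated, or that the form is certainly weekly. The primary analysis and the decision based on it are unaffected.

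**What to change.** - **Section 16.62:** replace the chi-square by a Wilcoxon rank-sum test (or a trend test) on one value per patient per cycle. Keep the frequency and percentage table by cycle and arm.
- **Section 16.62:** state whether the booklet or the phone call or visit supplies the cycle value, and how several answers in a cycle are reduced to one if the booklet is used.
- **Appendix V:** print one recall period. First reconcile the form with Section 4.0 and Appendix VI, then choose the period that matches how often the form is actually given. Choosing the past week for a form completed once per cycle would leave most of the cycle unasked.

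The cost is a sentence or two in 16.62 and one line on the form, with no new data and no change in sample size. The statistical price is less sensitivity to non-monotone differences, which the retained category table would still show.
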